4.2 Rationale for Study Design and Control Group

The original study, Study HGT-SAN-055, is an ongoing Phase I/II safety and ascending dose ranging study of IT administration of HGT-1410 via an IDDD, in patients 3 years of age and older with MPS IIIA and early cognitive impairment. This extension study is proposed to continue evaluation of the effects of IT HGT-1410 administration on long-term safety and clinical outcomes for patients who completed Study HGT-SAN-055 and elected to continue treatment with HGT-1410 in the HGT-SAN-067 study.

In order to traverse the blood-brain barrier, Shire is evaluating HGT-1410 delivered directly to the CNS using an IDDD. The advantage of using an IDDD is that it obviates the need for multiple lumbar punctures for drug delivery. Drug products will be administered through this port or, if the IDDD is non functional, via lumbar puncture.

If patients in the study require revision and/or replacement of the PORT-A-CATH IDDD, it will be removed and replaced with the SOPH-A-PORT Mini S device at a time judged appropriate by the investigator.

SOPH-A-PORT Mini S revision, implantation or explantation will be performed at the main site. However, if in the opinion of the investigator, emergency removal is clinically necessary, device explantation may be performed at the patient's local site.

4.3 Study Duration and Dates

The study duration allows patients who completed Study HGT-SAN-055 and elected to continue treatment with HGT-1410 in Study HGT-SAN-067 to receive treatment with HGT-1410 up to 8 years.

Patients with a partial or full device still in place after completion of the treatment period, may be followed for safety up to an additional 3 years or until the device is removed in the last patient.

The LPLV will be the safety follow-up visit after the final device (partial and/or full) is removed from the last patient during the safety follow-up period.

5 STUDY POPULATION SELECTION

5.1 Study Population

Patients who have completed all study requirements in Study-HGT-SAN-055 and who elected to continue HGT-1410 treatment will be eligible to participate; a maximum of 12 patients are planned for this study.

5.2 Inclusion Criteria

Each patient must meet the following criteria to be considered eligible for enrollment in this study.

1. The patient must have completed Study HGT-SAN-055 and, in the opinion of the investigator, have no safety or medical issues that contraindicate participation.
2. The patient, patient's parent(s) or legally authorized representative(s) has voluntarily signed an Institutional Review Board/Independent Ethics Committee-approved informed consent (and assent, if applicable) form after all relevant aspects of the study have been explained and discussed with them. Informed consent/assent must be obtained prior to any study specific procedures.
3. The patient has received at least 5 of the 6 planned infusions of HGT-1410 in the HGT-SAN-055 study.
4. The patient must be medically stable, in the opinion of the investigator, to accommodate the protocol requirements, including travel, assessments, and IDDD surgery (if necessary for replacement purposes), without placing an undue burden on the patient/patient's family.

5.3 Exclusion Criteria

Patients will be excluded from the study if there is evidence of any of the following:

1. The patient has experienced an adverse reaction to study drug in Study HGT-SAN-055 that contraindicates further treatment with HGT-1410.
2. The patient has a known hypersensitivity to the active ingredient or any excipients in HGT-1410 drug product.
3. The patient has significant non-MPS IIIA related central nervous system impairment or behavioral disturbances that would confound the scientific integrity or interpretation of study assessments, as determined by the investigator.
4. The patient has MPS IIIA behavioral-related issues, as determined by the investigator, which would preclude performance of study neurocognitive and developmental testing procedures.
5. The patient is pregnant, breast feeding, or is of childbearing potential who will not or cannot comply with the use of an acceptable method of birth control, such as condoms, barrier method, oral contraception, etc.
6. The patient has any known or suspected hypersensitivity to anesthesia or is thought to have an unacceptably high risk for anesthesia due to airway compromise or other conditions.
7. The patient has a history of a poorly controlled seizure disorder.

8. The patient is currently receiving psychotropic or other medications, which in the investigator's opinion, would be likely to substantially confound test results and the dose and regimen of which cannot be kept constant throughout the study.
9. The patient cannot sustain absence of aspirin, non-steroidal medications, or medications that affect blood clotting within 1 week prior to a relevant study-related procedure (eg, device re-implantation if applicable), or has ingested such medications within 1 week before any procedures in which any change in clotting activity would be deleterious.
10. The patient has received treatment with any investigational drug (other than HGT-1410) intended as a treatment for MPS IIIA within the 30 days prior to, during the study, or is currently enrolled in another study that involves an investigational drug or device (screening through safety follow-up contact).
11. The patient has received a hematopoietic stem cell or bone marrow transplant.

For patients to be implanted with the SOPH-A-PORT Mini S IDDD the following conditions are contraindicated, as described in the Instructions for Use:

1. The patient has had, or may have, an allergic reaction to the materials of construction of the SOPH-A-PORT Mini S device.
2. The patient's body size is too small to support the size of the SOPH-A-PORT Mini S Access Port, as judged by the investigator .
3. The patient has a known or suspected local or general infection.
4. The patient is at risk of abnormal bleeding due to a medical condition or therapy.
5. The patient has one or more spinal abnormalities that could complicate safe implantation or fixation.
6. The patient has a functioning CSF shunt device.
7. The patient has shown an intolerance to an implanted device.

6 STUDY TREATMENT(S)

6.1 Description of Treatment(s)

6.1.1 Study Drug

Recombinant human heparan N-sulfatase (HGT-1410 drug product) formulation is a sterile solution for injection in single-use vials for IT administration. It is formulated in an aqueous isotonic solution containing 15.0 mg/mL HGT-1410 in 145 mM sodium chloride, 0.02% (v/v) polysorbate 20, 5 mM sodium phosphate at pH 7.0.

6.1.2 Intrathecal Drug Delivery Device

The PORT-A-CATH will continue to be used for the administration of drug product for each patient until such time as an IDDD replacement may be required. Following implementation of protocol Amendment 4, any replacements will be performed using the SOPH-A-PORT Mini S.

After IDDD replacement the drug product will be administered via the SOPH-A-PORT Mini S Implantable Access Port. The SOPH-A-PORT Mini S device is intended for long-term, intermittent access to the IT space for the delivery of investigational drug.

The SOPH-A-PORT Mini S is comprised of the following 7 components:

- One SOPH-A-PORT Mini S Access Port
- One intrathecal port closed-tip catheter
- One guidewire
- Two suture wings
- One 14-gauge Tuohy needle
- One 22-gauge non-coring Huber needle
- One Luer lock Connector.

Further details are provided in the Instructions for Use.

6.1.3 Placebo or Control

This study will not employ a placebo or control.

6.2 Treatment Administered

HGT-1410 for IT administration will be provided by Shire. HGT-1410 will be administered by an IDDD. Following the review and signing of informed consent (and assent, if applicable), eligible patients will initially receive the same dose of HGT-1410 they received in Study HGT-SAN-055:

- Group 1: HGT-1410 administered by IT injection 10 mg once per month (Q4W)
- Group 2: HGT-1410 administered by IT injection 45 mg once per month (Q4W)
- Group 3: HGT-1410 administered by IT injection 90 mg once per month (Q4W)

Patients assigned to Group 1 had their dose increased to 45 mg once per month (Q4W) at the first administration of HGT-1410 following full approval of protocol Amendment 4.

The study drug will be administered through an IDDD.

The initial implantation and revision and/or explantation of the PORT-A-CATH IDDD or SOPH-A-PORT Mini S will be performed by pediatric or general neurosurgeons or anesthesiologists who have experience in port and catheter implant procedures and intrathecal-access procedures. Please refer to the relevant IFU for further details.

Drug administration will be performed in a clinical setting by appropriately trained and skilled healthcare providers (nurses or physicians) with knowledge of the patient's drug regimen and experienced in accessing vascular or CNS ports or CNS infusion pumps. Patients and patients' families will not be directly using the device to administer drugs and will have limited direct interaction with the device as there is minimal care required during the immediate postoperative period as the implant site heals, or at times of drug administration.

As previously noted in Section 4.1, under the appropriate conditions, IT HGT-1410 may be administered at local sites rather than main sites to reduce the burden of monthly travel.

6.3 Selection and Timing of Dose for Each Patient

Patients will check into the study center 1 day prior to IT HGT-1410 dosing for safety assessments, designated Day 1, on each HGT-1410 treatment week, and if no safety concerns exist, will receive IT administration of HGT-1410 on Day 2 (± 2 days). However, if feasible and there are no safety concerns in the opinion of the investigator, the Day 1 and Day 2 assessments and dosing may be combined and performed on Day 2; if this is done the results will be recorded as Day 2. Patients will remain in the study center for at least 4 hours following dosing with HGT-1410 and will be discharged from the unit when deemed clinically stable by the investigator.

The IT injections are to be administered every 28 days (± 7 days). If a patient's IDDD becomes nonfunctional, it may be revised (partial or complete) (a maximum of twice in a 6 month period) so that the patient can remain on study (see Section 7.12 for details).

6.3.1 Cerebral Spinal Fluid Sample Procedure

CSF samples will be obtained prior to each injection for clinical laboratory evaluation and potential biomarker studies. The IDDD will be used for CSF sampling and a topical anesthetic agent may be applied over the skin covering the IDDD reservoir prior to sampling. Site personnel should refer to the operations manual for instructions on the use of topical anesthesia prior to accessing the IDDD reservoir.

If use of the IDDD is precluded on a scheduled day of dosing, CSF samples may be obtained by LP, as described in the IDDD Manual and Section 6.3.2. Intrathecal Administration of HGT-1410.

A visual examination of both the port and catheter track will be performed before each IT injection.

HGT-1410 will be administered using an IDDD. After appropriate pre-procedure assessments are completed, anesthesia cream will be applied to the skin over the port. Patients may receive sedation as necessary to alleviate anxiety and/or to facilitate drug delivery.

Patients will receive HGT-1410 via slow push/injection through an appropriately sized syringe (see the Pharmacy Manual). Replacement of fluid, including drug, to the CSF will be an approximate equal volume to that removed. The patient's vital signs will be continuously monitored. The patient will also be monitored closely during study drug administration and through the next 4 hours for any adverse clinical reactions. The patient will be encouraged to lie down comfortably for 1 to 3 hours post injection, although this may be difficult for the most hyperactive patients.

For the Soph-A-Port Mini S, a 22-gauge Huber non-coring needle is to be used for access to the implanted port; standard hypodermic needles would damage the septum and may cause leakage. If no needle-free connector is present, either a stopcock of the Huber needle infusion set's clamp is to be used to prevent CSF backflow and to mitigate the risk of air entering the system. It is possible to use other brands of Huber non-coring needles, provided that their specifications are identical to that of the Huber needle supplied by Sophysa in the SOPH-A-PORT Mini S (22G).

The injection date, injection start/stop time, planned dose, injection volume, and flush volume will be recorded on the patient's eCRF.

In the event of IDDD malfunction, CSF collection and study drug administration may be performed via LP (see Section 6.3.2). The investigation and management of a malfunctioning IDDD is detailed in the PORT-A-CATH or SOPH-A-PORT IFUs. Partial or complete replacement of the IDDD may be necessary (only permitted twice in a 6-month period, including the time a patient was in study HGT-SAN-055), and will require scheduling of the appropriate procedure. The definitive diagnosis of the cause of IDDD failure may not be possible until the time of exploratory surgery. Surgery will take place at the earliest convenience, so the patient may remain on, or as close as possible to their treatment schedule.

6.3.2 Administration of HGT-1410 via Lumbar Puncture Guidance Concerning Performance of Lumbar Puncture for Study Drug Administration and Cerebrospinal Fluid Sample Collection

It is intended that the IDDD will be used to deliver all IT injections of study drug and to obtain CSF samples. If the IDDD appears to be nonfunctional, or if its use is precluded on a scheduled day of dosing, site personnel will refer to the IDDD manual (s), which provides details on the investigation and management of any IDDD-related issues. This may include possible partial revision or complete replacement of the IDDD as indicated. If the nonfunctional IDDD is a PORT-A-CATH device, then it will be replaced by a SOPH-A-PORT Mini S device.

If there are medical contra-indication to the re-implantation of a new device, or if the patient so desires, repeat monthly lumbar punctures may be considered as an alternative way of delivering

the study drug and obtaining CSF samples under limited circumstances. If no safety risks are identified by the investigator, up to 12 consecutive lumbar punctures may be performed across studies HGT-SAN-055 and HGT-SAN-067. Once a patient has reached the maximum of 12 consecutive lumbar punctures, a new IDDD will be re-implanted for subsequent dosing, unless, in the opinion of the investigator and medical monitor, assessment of risk/benefit favors continued dosing via lumbar puncture.

Continued treatment via repeat lumbar puncture beyond the stipulated 12 consecutive monthly doses can be considered only in individual cases of patients where this treatment is very well tolerated and the investigator has not identified any safety concerns associated with repeat lumbar puncture and repeat sedation/anesthesia.

6.4 Method of Assigning Patients to Treatment Groups

This is an open-label, non-randomized study; all patients enrolled in this study will be treated with HGT-1410. Patients will initially receive the same dose of HGT-1410 they received in Study HGT-SAN-055. Patients assigned to Group 1 (10 mg once per month [Q4W]) had their dose increased to 45 mg once per month (Q4W) at the first administration of HGT-1410 following full approval of protocol Amendment 4.

6.5 Blinding

Not applicable; as this trial is not blinded.

6.6 Concomitant Therapy

All non-protocol treatments and procedures that occur from the time of informed consent (and assent, if applicable) through the safety follow-up contact are regarded as concomitant and will be documented on the appropriate pages of the eCRF. Concomitant therapy includes medications (including Genistein), therapies/interventions administered to patients, and medical/surgical procedures performed on the patients.

Every effort should be made to keep the patient's symptomatic Sanfilippo syndrome Type A treatment constant throughout the study. However, changes in medications are acceptable if necessary according to clinical judgment. All changes will be recorded on the appropriate eCRF. Concomitant medication will be coded using World Health Organization Drug Dictionary (WHO-DD).

6.7 Restrictions

6.7.1 Prior Therapy

Prior therapy excluded for this study consists of the following:

- Psychotropic or other medications, which in the investigator's opinion would be likely to substantially confound test results, and the dose and regimen of which cannot be kept constant throughout the study.

- The patient cannot sustain absence from aspirin, non-steroidal medications, or medications that affect blood clotting within 1 week prior to a relevant study related procedure (eg, device implantation if applicable) or medications within 1 week before any procedures in which any change in clotting activity would be deleterious.
- The patient has received any investigational drug or device intended as a treatment for MPS IIIA within the 30 days prior to the study other than HGT-1410 or is enrolled in another study that involves an investigational drug or device.
- Hematopoietic stem cell or bone marrow transplant.

6.7.2 Fluid and Food Intake

Food and fluid intake are not restricted over the course of the study, with the exception of hospital standard pre-anesthesia dietary restrictions.

6.7.3 Patient Activity Restrictions

For patients implanted with the SOPH-A-PORT Mini S please refer to the SOPH-A-PORT Mini S IFU for details regarding patient activity restrictions for patients to be implanted with this device.

6.8 Treatment Compliance

HGT-1410 is administered under controlled conditions by the investigator; therefore, full patient compliance with study treatment is anticipated in this study.

6.9 Packaging and Labeling

6.9.1 Drug Product

Drug product will be supplied in a 3 mL clear, colorless glass (Type 1) vial. Each vial holds an extractable volume of 1 mL of HGT-1410. The closure is a gray, 13 mm stopper composed of butyl rubber with a fluoro resin lamination. The overseal is an aluminium seal with a flip-off, plastic, tamper evident cap.

See the Pharmacy Manual for additional details.

6.9.2 SOPH-A-PORT Mini S Access Port

The SOPH-A-PORT Mini S Access Port is available in one size, individually packaged, with other SOPH-A-PORT Mini S components in double peel-off, sterile, pyrogen-free packaging, sterilized with Ethylene Oxide. Instructions for use are also included in the packaging. A guidewire is provided in separate double pouch, sterile, pyrogen-free packaging.

Labels are provided on the outer carton, and on both the SOPH-A-PORT Mini S box and guidewire/cannula package inside.

6.10 Storage and Accountability

6.10.1 Investigational Product

Drug product should be stored refrigerated (2°C to 8°C); drug product may not be stored beyond the expiration date on the vial.

All HGT-1410 study drug delivered to an investigator will be recorded and accounted for throughout the study. All HGT-1410 study drug must be recorded on a patient-by-patient basis. The lot number of the IDDD and the date and time of administration of the study medication will be documented on the appropriate eCRF.

All unused study medication and other study materials are to be returned to the sponsor or its designee or disposed of after sponsor approval per site policy after study completion.

6.10.2 Intrathecal Drug Delivery Device

6.10.2.1 PORT-A-CATH IDDD

Please refer to the operations manual for return instructions.

6.10.2.2 SOPH-A-PORT Mini S IDDD

The disposition of all SOPH-A-PORT Mini S intrathecal drug delivery devices delivered to a principal investigator must be recorded on a patient-by-patient basis by completing the Accountability Log. The date and time of administration of the investigational product and use of the SOPH-A-PORT Mini S device must be documented on the patient's appropriate eCRF.

The principal investigator, clinical research coordinator, or designee (eg, pharmacist) must ensure that all documentation regarding receipt, storage, dispensing, loss/damaged SOPH-A-PORT Mini S intrathecal drug delivery devices and return of used/unused intrathecal drug delivery devices) is complete, accurate, and ready for review at each monitoring visit and/or audit. The sites must ensure that the SOPH-A-PORT Mini S devices are available for the monitor to inventory and prepare for return shipment to the sponsor or designee, if required.

The SOPH-A-PORT Mini S and its components are sterile, single-use devices.

Please refer to the relevant IDDD Manual for device return instructions.

6.11 Investigational Product Retention at Study Site

All HGT-1410 study drug delivered to an investigator will be recorded and accounted for throughout the study. All HGT-1410 study drug must be recorded on a patient-by-patient basis. The lot number of the IDDD and the date and time of administration of the study medication will be documented on the appropriate eCRF.

All unused study medication and other study materials are to be returned to the sponsor or its designee or disposed of after sponsor approval per site policy after study completion.

7 STUDY PROCEDURES

7.1 Informed Consent

Study procedures will be conducted only after written informed consent for the patient to participate in this study is provided by the parent(s) or the patient's legally authorized representative(s) and assent from the patient (if applicable). Detailed descriptions of patient evaluations required for this protocol are described in this section. These evaluations will be performed during the indicated days and weeks of each study month (see Appendix 1, [Table A1-1](#) and [A1-2](#) Schedule of Events).

All data collected are to be recorded on the appropriate eCRF. Blood, urine and CSF volumes to be collected for each clinical laboratory measurement are described in detail in the Laboratory Manual.

After the treatment period ends, informed consent from patients who do not have the IDDD removed (partial or full device) will be obtained for the safety follow-up period.

7.2 Physical Examination

A full physical examination or a symptom-directed physical examination of each patient will be performed at time points detailed in Appendix 1, [Table A1-1](#) Schedule of Events, for the duration of the treatment period. The physical examinations for the safety follow-up period will be symptom-directed, see Appendix 1, [Table A1-2](#) Schedule of Events, for details.

Any changes from the screening physical examination will be captured as AEs in the eCRF. If the patient experiences an AE associated with genitourinary evaluation, the patient may have the genitourinary evaluation performed by their primary care provider and a follow-up report will be sent to the investigator. Therefore, the genitourinary evaluation may not need to be performed again if the examination occurred within the visit window for that time point.

Note: if the patient's hearing cannot be assessed during the physical examination, the patient will have an Ears, Nose, and Throat Evaluation performed under anesthesia at the screening/start of study visit. If it is determined that the patient requires pressure-equalization (PE) tubes, they may be implanted during that evaluation (see Section [7.9](#)). Note: PE tubes may be re-implanted if they fall out during this study.

The physical examination findings will be recorded on the eCRF and will include a review of the patient's general appearance as well as the following evaluations:

- Head and neck
- Eyes, ears, nose, and throat
- Chest and lungs
- Cardiovascular
- Abdomen
- Skin
- Lymphatic
- Musculoskeletal
- Neurological (symptom directed and at least every 12 months)
- Endocrine
- Genitourinary (as per referring physician)

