3 STUDY ENDPOINTS

3.1 Primary Endpoint

The primary endpoints of this study are related to the long-term safety of intrathecal HGT-1410 administration. The safety endpoints are:

[figure not shown]
- adverse events (type and severity)
- changes in clinical laboratory testing (serum chemistry including liver function tests, hematology, and urinalysis)
- electrocardiograms (ECG)
- CSF chemistries (including cell counts and inflammatory markers)
- anti-rhHNS antibodies (in CSF and serum).

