7.22 Adverse Events

7.22.1 Definitions of Adverse Events and Serious Adverse Events

7.22.1.1 Adverse Event

An AE is any noxious, pathologic, or unintended change in anatomical, physiologic, or metabolic function as indicated by physical signs, symptoms, or laboratory changes occurring in any phase of a clinical study, whether or not considered study drug-related. This includes an exacerbation of a pre-existing condition. Once the informed consent is signed and dated, any adverse event prior to the start of study drug must be reported.

AEs include:

- Worsening (change in nature, severity, or frequency) of conditions present at the onset of the study
- Intercurrent illnesses
- Drug interactions

- Events related to or possibly related to concomitant medications
- Abnormal laboratory values (this includes significant shifts from baseline within the range of normal that the investigator considers to be clinically important)
- Clinically significant abnormalities in physical examination, vital signs, and weight

Throughout the study, the investigator must record all AEs on the AE eCRF, regardless of the severity or relationship to study drug. The investigator should treat patients with AEs appropriately and observe them at suitable intervals until the events stabilize or resolve. AEs may be discovered through observation or examination of the patient, questioning of the patient, complaint by the patient, or by abnormal clinical laboratory values.

In addition, AEs may also include laboratory values that become significantly out of range. In the event of an out-of-range value, the laboratory test should be repeated until it returns to normal or can be explained and the patient's safety is not at risk.

All AEs should be recorded with causality assessment.

The information presented below is intended to provide issues to consider for AEs associated with intrathecal injections of HGT-1410. In general, these AEs can be classified as follows:

- Adverse events due to systemic exposure to HGT-1410 caused by the drug diffusion from the CSF to the peripheral circulation;
- Adverse events related to the direct delivery of HGT-1410 to the intrathecal CSF space and meninges, and subsequent diffusion into brain parenchyma, via an intrathecal route
- IDDD-related AEs

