8.1 Screening Visit/Study Start Visit – Main Site

All Screening assessments for this study are to have been performed during the Week 26 EOS procedures in HGT-SAN-055 (ie, 30 [\pm 7] days after the last HGT-1410 administration). If less than 60 days have elapsed since completion of the EOS assessments for HGT-SAN-055, and the start of HGT-SAN-067, the assessments detailed in this Screening visit do not need to be repeated. The Baseline visit for this study will be the first day the patient received their first dose of HGT-1410 in the HGT-SAN-055 Study.

If more than 60 days have elapsed following the HGT-SAN-055 EOS procedures, patients will be evaluated for enrollment in HGT-SAN-067 on a case-by-case basis by the investigator. A decision about enrollment will be made following discussion with the medical monitor. If the patient is enrolled, the following assessments are to be repeated within 30 days prior to the first scheduled intrathecal HGT-1410 dose:

- Physical examination
- Height and weight
- Head circumference
- ECG
- Vital signs
- Hematology
- Leukocyte pellet preparation to be used for additional disease-related laboratory studies, including possible assessment of cross-reactive immunologic material (if this is not collected at baseline, it can be collected at any subsequent pre-dosing time point)
- Serum chemistry
- Pregnancy testing (for post menarche premenopausal females only)
- Urinalysis
- Urine GAG, including heparan sulfate and heparan sulfate derivatives
- Plasma collection for biomarkers
- Anti-rhHNS antibody testing (serum and CSF)
- General anesthesia: administration of anesthesia will be given prior to the following assessments:
 - ABR
 - MRI of the head
 - Neurological examination (performed prior to the administration of anesthesia)

- Full Neurodevelopmental assessments, including Vineland Adaptive Behavior Scales, Second Edition (VABS-II; all assessments performed prior to the administration of anesthesia)
- CSF sample collection (chemistry, cell count, heparan sulfate and heparan sulfate derivatives, and other MPS exploratory biomarkers) via the IDDD
- Children's Sleep Habits Rating Scale
- CHQ-50
- CHQ-87
- ITQOL
- Concomitant medications, therapies, and procedures
- AE assessments

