10.6 Efficacy, Safety, and Pharmacodynamic Evaluations

10.6.1 Primary Analyses

10.6.1.1 Safety Analysis

In general, safety assessments will be based on all assessments post-baseline. The assessment of safety will be based primarily on the frequency of AEs, and on the frequency of clinically notable abnormal vital sign and laboratory values. Changes from baseline will be calculated by subtracting the baseline value from the post-baseline value.

All enrolled patients who had an IDDD surgical procedure and/or received administration of HGT-1410 will be included in the safety analysis.

Adverse events will be recorded throughout the study and at early termination. Adverse events and medical conditions will be coded using the Medical Dictionary for Regulatory Activities (MedDRA).

Adverse events will be summarized by presenting, for each dose group during the treatment period, the number and percentage of patients having any AE, having an AE in system organ class, and having each individual AE. In addition, those events which resulted in death or were otherwise classified as serious will be presented in a separate listing. The incidence of treatment-emergent adverse events, defined as all AEs from the time of the surgery for IDDD implantation to the last follow up contact, ie, 30 days after the last HGT-1410 administration, (new or worsened from baseline) during the treatment period, will be summarized by system organ class, severity, type of adverse event and relationship to trial medication/procedure.

Treatment-emergent AEs, of the treatment period, deemed related to HGT-1410 administration will be summarized separately.

IDDD and procedure-related AEs will be summarized within system organ class by preferred term. IDDD and procedure-related AEs will be tabulated by severity (mild, moderate, severe) and degree of relatedness. Separate tabulations will be provided for adverse events related to the IDDD, device surgical procedure (including post-implant infections) and IT administration process. These summaries will be presented by device and overall, as appropriate.

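### Section 7.2 makes any change from the screening physical examination an adverse event, which contradicts the narrower AE definition in Section 7.22.1.1

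*Protocol*

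**What the plan says.** Section 7.2 of the Protocol (Physical Examination) gives the recording rule: "Any changes from the screening physical examination will be captured as AEs in the eCRF". The examination covers general appearance and a list of 11 further items, among them abdomen, musculoskeletal, endocrine and genitourinary.

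Section 7.22.1.1 defines the AE itself: "An AE is any noxious, pathologic, or unintended change in anatomical, physiologic, or metabolic function". Among its inclusions are "Worsening (change in nature, severity, or frequency) of conditions present at the onset of the study" and "Clinically significant abnormalities in physical examination, vital signs, and weight".

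Section 3.1 puts "adverse events (type and severity") first among the primary safety endpoints.

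On timing, Section 8.1 says "All Screening assessments for this study are to have been performed during the Week 26 EOS procedures in HGT-SAN-055", so the screening examination falls at about Month 6. The same section adds: "The Baseline visit for this study will be the first day the patient received their first dose of HGT-1410 in the HGT-SAN-055 Study".

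Section 10.6.1.1 plans a summary, by dose group during the treatment period, of patients with any AE, with an AE in each system organ class and with each individual AE. It plans a separate treatment-emergent summary, restricted to events "new or worsened from baseline".

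**The concern.** The two sections give sites different instructions for the same observation. Under 7.2 the trigger is any difference from one fixed examination. Under 7.22.1.1 the trigger is harm, worsening or a clinically significant abnormality. Two sites can both comply with the protocol and send different AE records to the database.

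The protocol's own description of the disease and population makes the difference foreseeable. Section 1.1 reports that liver and spleen enlargement in this disease is transient in childhood. The children are followed for years in which puberty can begin. Both are changes from screening, and neither need be harmful.

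At stake is the consistency of the AE frequencies, which are the main output of a descriptive safety study. An analysis plan can filter tables, but it cannot make sites apply one rule when they decide what to enter.

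**Working it through.** There is no planned figure to reproduce: Section 10.2 makes no sample size calculation. The check is a comparison of texts, with some counting.

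**1. The capture rules side by side.**

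| Observation on examination | 7.2 read literally | 7.22.1.1 |
|---|---|---|
| New, clinically significant abnormality | AE | AE |
| Worsening of a condition present at study onset | AE | AE |
| Enlarged liver or spleen at screening that later regresses | AE | Not an AE |
| Normal pubertal change (endocrine or genitourinary item) | AE | Not an AE |
| Trivial change without clinical importance | AE | Not listed as an AE for physical examination |

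The rules agree on the first two rows and part on the other three. For laboratory values, too, 7.22.1.1 counts a shift within the normal range only if the investigator considers it clinically important. The absence of any threshold in 7.2 is therefore out of line with the rest of the definition.

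**2. Whether the divergent cases can occur.** Section 4.2 gives the age at entry to the parent study as 3 years and older. Month 102 is 102 / 12 = 8.5 years after the first dose, so the youngest possible entrant would be about 3 + 8.5 = 11.5 years old, and others older. Table A1-1 (footnote p) schedules full examinations monthly to Month 54 and then at Months 66, 78, 90 and 102. Counting calendar months, that is 48 (Months 7 to 54) + 4 = 52 per patient, each compared with the same screening examination. Not every item is examined each time: the neurological item is symptom-directed with a yearly minimum, and the genitourinary item is left to the referring physician.

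**3. Where such records would go.** The any-AE, system organ class and individual-term summaries in 10.6.1.1 state no new-or-worsened condition, so an improvement recorded as an AE would be counted there and listed. The treatment-emergent summary does carry that condition, and improvement should not pass it. A pubertal sign is new since baseline, so the wording of the filter alone would not remove it.

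**4. How coarse the percentages are.** With at most 12 patients, one patient is 1 / 12 = 8.3 percentage points of the whole study. If the three dose groups held 4 patients each (an assumption; the protocol gives no group sizes), one patient would be 1 / 4 = 25 points of a group. This holds for any AE in so small a study. It shows how visible one extra term is, not how many there would be.

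**The case against.** The strongest reply is that 7.22.1.1 is the protocol's AE definition and an experienced site would read 7.2 in its light. The study is descriptive and tests no prior hypothesis. Treatment-emergent events are also summarized by severity and relationship, and all safety data are listed, so benign entries would be visible and over-recording would conceal no harm. This limits the consequence. It does not remove the contradiction, because nothing tells sites to subordinate 7.2.

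Three stronger readings are tempting, and the documents do not support them.

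- A reader might infer that improvement, growth and puberty will certainly enter the primary endpoint. That depends on which section a site follows. Growth is a weak example: height, weight and head circumference are separate procedures (Sections 7.3 and 7.4) outside the 7.2 list.
- A reader might infer that measuring change from Month 6 while the analysis uses the first parent-study dose leaves a gap, so that an abnormality arising in between and persisting is lost. Section 4.1 covers this: AEs ongoing from HGT-SAN-055 stay recorded there and are reported as concurrent conditions in the extension's eCRFs. Recording what is new in the extension and comparing with baseline in the analysis are separate steps and may have separate reference points.
- A reader might try to put a number on the surplus records. The documents give no rate of benign changes, 12 is a maximum, treatment is for up to 8 years, and required full examinations become about yearly after Month 54. Any total would be a guess.

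**Conclusion.** The contradiction is real: 7.2 and 7.22.1.1 set different recording rules for the first-listed primary endpoint. If 7.2 is followed literally, favourable and normal developmental changes become AEs and reach the all-AE summaries, the per-term summaries and the listings. AE recording could then differ between sites and be inflated. The size cannot be estimated from the documents. It depends on how sites have read 7.2 and how often benign changes occur, and neither is stated. The case for AE tables that cannot be interpreted is not made, and no sample size or error rate is affected. The point is modest in consequence and cheap to correct.

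**What to change.** Replace the sentence in 7.2 with: *Any new or worsened finding relative to the screening physical examination that meets the AE definition in Section 7.22.1.1 (clinically significant abnormality) will be captured as an AE; other changes are recorded on the physical examination eCRF page only.*

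Keep screening as the reference for capture. Making the first HGT-SAN-055 dose the reference would invite a second recording of abnormalities that arose in the parent study and persist. Leave those to the carry-over rule in Section 4.1, and leave the comparison with baseline to the treatment-emergent analysis in 10.6.1.1.

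For records already entered, have the medical monitor flag examination-derived AEs that do not meet 7.22.1.1, and show the AE tables with and without them.

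The cost is one sentence in an amendment and one medical review of a limited set of records. Examination findings stay on the eCRF, so no data are lost. The small downside is that AE counts may fall, and the report must describe both rules.
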